1.2 Synopsis

AbbVie Inc.	Protocol Number: M12-927
Name of Study Drug: Levodopa-Carbidopa intestinal gel (SLV-187)	Phase of Development: 3b
Name of Active Ingredient: Levodopa-Carbidopa	Date of Protocol Synopsis: 31 May 2017

Protocol Title: An Open-label, Randomized 26-Week Study Comparing Levodopa-Carbidopa INteStInal Gel (LCIG) Therapy to Optimized Medical Treatment (OMT) on Non-Motor Symptoms (NMS) in Subjects with Advanced Parkinson's Disease – INSIGHTS Study
	

Objectives:
 
Primary The primary objective of this study is to examine the effect of LCIG relative to that of OMT on non-motor symptoms associated with advanced Parkinson's disease (PD) as assessed by the Non-Motor Symptoms Scale (NMSS) Total Score and the Modified Parkinson's Disease Sleep Scale (PDSS-2) Total Score.
 
Secondary To assess the effect of LCIG relative to that of OMT on the motor symptoms/motor complications, safety, tolerability and health-related outcome measures.
 
Motor symptoms/motor complications will be measured by:
 
 • Unified Parkinson's Disease Rating Scale (UPDRS) Parts III and IV 
Safety and tolerability will be assessed by:
 
 • Adverse event monitoring • Neurological exams • Clinical laboratory evaluations • Electrocardiogram • Vital signs and weight • Columbia Suicide Severity Rating Scale (C-SSRS) • Minnesota Impulsive Disorders Interview (MIDI) • Sleep Attacks Questionnaire (SAQ) 
Health Related Outcomes will be measured by:
 
 • Parkinson's Disease Questionnaire-8 (PDQ-8) • Clinical Global Impression of Change (CGI-C) • UPDRS Parts I and II • Patient Global Impression of Change (PGIC) • Parkinson Anxiety Scale (PAS) • Geriatric Depression Scale (GDS-15) • King's Parkinson's Disease (PD) Pain Scale 	
Investigators: Multi-center	

Study Sites: This study will be conducted at approximately 40 – 50 sites in approximately 10 countries worldwide

Study Population:

Levodopa-responsive Parkinson's disease patients with severe motor fluctuations and hyperkinesia/dyskinesia when available combinations of Parkinson medicinal products have not given satisfactory results.

Number of Subjects to be Enrolled: Approximately 88 subjects (44 per each treatment group)

Methodology:

[figure not shown]

Figure 1: Study Design Schematic

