The efficacy analysis will be performed on the intent-to-treat dataset which will include all subjects who are randomized to the optimized medical treatment, and all subjects who are randomized to LCIG and received at least one dose of study drug. For assessments of efficacy the treatment period will begin the day after randomization (V3) for subjects randomized to OMT, and the day of first LCIG infusion following PEG-J placement for subjects randomized to LCIG treatment. The treatment period will end on the day of the final visit for subjects randomized to OMT, and on the last day of LCIG study drug infusion for subjects randomized to LCIG treatment. The last assessment prior to randomization will be considered baseline and the last assessment that is no more than 2 days after the end of the treatment period will be considered the final evaluation.

Statistical Methods (Continued):

Efficacy (Continued):

Primary Efficacy Analysis

There are 2 alternative primary efficacy variables, change from baseline to Week 26 for NMSS total score and change from baseline to Week 26 for PDSS-2 total score. Either variable considered statistically significant after multiplicity adjustment is sufficient to declare success of the study.

The primary efficacy analysis model is a likelihood-based mixed-effects model repeated measures (MMRM) analysis of the change from baseline for each post-baseline observation using all observed data. The model will include fixed, categorical effects for treatment, site, visit, and treatment-by-visit interaction, with continuous fixed covariates for baseline score and the baseline score-by-visit interaction. The primary comparison will be the contrast between LCIG and optimized oral treatment at the Week 26 Visit.

The two-sided P values obtained from the MMRM model for NMSS total score change from baseline to Week 26 and PDSS-2 total score change from baseline to Week 26 will be adjusted for multiplicity using the Hochberg procedure. This method controls the family-wise error rate (FWER) at a pre-specified significance level ($\alpha = 0.05$). Specifically, the following steps will be followed:

- If the larger of the 2 P values is ≤ 0.05 (i.e., both P values are ≤ 0.05), both endpoints are considered statistically significant.

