5.0 Investigational Plan

5.1 Overall Study Design and Plan: Description

This is a Phase 3b, open-label, multicenter 26-week study comparing LCIG to OMT on NMS associated with advanced PD. This study will be conducted at approximately 40 – 50 sites that specialize in movement disorders in approximately 10 countries.

Figure 2. Study Design Schematic

The study is designed to enroll an adequate number of subjects such that approximately 88 subjects will be randomized in a 1:1 ratio to either treatment group of OMT or LCIG in order to meet scientific and regulatory objectives without over-enrolling an undue number of subjects in alignment with ethical considerations.

The study will consist of 3 sequential periods: Screening, Treatment and Follow-Up.

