8.1.3.1 Primary Efficacy Analysis

There are 2 alternative primary efficacy variables, change from baseline to Week 26 for NMSS total score and change from baseline to Week 26 for PDSS-2 total score. Either variable considered statistically significant after multiplicity adjustment is sufficient to declare success of the study.

NMSS Total Score

The NMSS was developed to assess non-motor symptoms in PD. It is obtained through interview and rated by health professionals. It contains 30 questions grouped into 9 domains: cardiovascular (2 items), sleep/fatigue (4 items), mood/cognition (6 items), perceptual problems/hallucinations (3 items), attention/memory (3 items), gastrointestinal tract (3 items), urinary (3 items), sexual function (2 items), and miscellaneous (4 items). Each question is scored with respect to severity and frequency. Severity is rated on a

scale where 0 = none, 1 = mild, 2 = moderate and 3 = severe. Frequency is rated on a scale where 1 = rarely, 2 = often, 3 = frequent and 4 = very frequent. Item scores are calculated as the product of severity and frequency. Domain scores and a total score are obtained by summing the item scores.

PDSS-2 Total Score

The PDSS-2 was developed from the PDSS based upon the need for a treatment-measuring tool containing PD-specific sleep disorders. The instrument was extended to address specific sleep disturbances such as RLS, akinesia, pain, and sleep apnea. The frequency is assessed for the 15 sleep problems based on a 5-point Likert-type scale (ranging from 0 [never] to 4 [very often]). Scores are calculated for each domain as well as a total score.

Primary Analysis Model and Multiplicity Adjustment

The primary efficacy analysis model is a likelihood-based mixed-effects model repeated measures (MMRM) analysis of the change from baseline for each post-baseline observation using all observed data. The model will include fixed, categorical effects for treatment, country, visit, and treatment-by-visit interaction, with continuous fixed covariates for baseline score and the baseline score-by-visit interaction. The primary comparison will be the contrast between LCIG and optimized oral treatment at the Week 26 Visit.

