8.2 Determination of Sample Size

Approximately 88 subjects will be enrolled into the study and randomized in a 1:1 ratio to either optimized medical treatment or LCIG. There are no results on NMSS or PDSS-2 available from randomized trials comparing LCIG and OMT. Interim data from ongoing Phase 3b Study M12-920 showed that the improvement in NMSS total score from baseline to Week 12 is 24.8 in the LCIG group with standard deviation of 24. Results from Zibetti et al (2013) showed that the improvement in PDSS-2 total score after an average of 3.5 months of LCIG treatment was 13.1. The standard deviation was not provided and is estimated to be 12.2 assuming the correlation between baseline and follow-up visits is 0.5.

The significance level for this study is 0.05. For sample size determination, it is assumed that the improvement in the OMT group is 33% of the LCIG group, i.e., the improvement is 8.2 on NMSS total score and 4.3 on PDSS-2 total score, and that the correlation between these 2 measures is 0.5. Simulation showed that a study with 37 subjects per group will have 90% power to declare statistical significance on at least one of these 2 alternative primary endpoints after multiplicity adjustment using Hochberg procedure. It is further assumed that 10% of randomized subjects in either treatment group will not provide post-randomization efficacy assessment. Additional simulations showed that 44 subjects per group will provide 90% power in the sensitivity analysis using baseline observation carried forward for subjects without post-randomization assessment. Therefore the total planned enrollment is decided to be 88 subjects.

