8.3 Randomization Methods

Approximately 88 subjects will be enrolled into the study and randomized in a 1:1 ratio to either optimized medical treatment or LCIG at the end of Visit 3. Subject randomization will be stratified by country.

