The primary efficacy variables will be the change from baseline to Week 26 in the NMSS and PDSS-2 total scores. They will each be estimated using PROC MIXED and a mixed-effect repeated measures model (MMRM) for the change from baseline to each scheduled visit. The model will include the fixed effects of treatment, country and visit, with baseline score as a covariate, and the baseline score-by-visit interaction. The unstructured covariance structure will be used to estimate the within subject variance-covariance structure and Satterthwaite's approximation will be used to estimate the denominator degrees of freedom. If the model fails to converge, the first order autoregressive (AR[1]) covariance structure will be substituted. If the model still fails to converge, the compound symmetry (CS) covariance structure will be substituted. Type III sum-of-squares and least-square (LS) means will be used for statistical evaluations. The LS mean and 95% confidence interval obtained from the model will be presented. The primary comparison will be the contrast between LCIG and optimized medical treatment at the Week 26 Visit. The primary null and alternative hypotheses may be expressed as:

$$H_0: \mu_{\text{LCIG}} = \mu_{\text{OMT}}$$

$$H_A: \mu_{\text{LCIG}} \neq \mu_{\text{OMT}}$$

Where μ_{LCIG} is the mean change from baseline to Week 26 for LCIG group in the NMSS (or PDSS-2) total score and μ_{OMT} is the mean change from baseline to Week 26 for OMT group in the NMSS (or PDSS-2) total score. The statistical tests at other visits will be considered secondary.

The change in the NMSS (or PDSS-2) total score to each planned visit and to the final visit will also be summarized by the following descriptive statistics: number of non-

missing observations, mean baseline score and standard deviation, mean visit score and standard deviation, median visit score and range, mean change from baseline and its standard deviation and standard error, median change from baseline and range. The hypothesis of change from baseline will be evaluated at each visit with a one-sample t-test.

The two-sided P values obtained from the MMRM model for NMSS total score change from baseline to Week 26 and PDSS-2 total score change from baseline to Week 26 will be adjusted for multiplicity using the Hochberg procedure. This method controls the family-wise error rate (FWER) at a pre-specified significance level ($\alpha = 0.05$). Specifically, the following steps will be followed:

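### The synopsis puts site in the primary MMRM where the protocol body, the SAP and the stratification use country: a minor correction to make before database lock

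*Protocol*

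**What the plan says.** Protocol 1.2 (Synopsis, Primary Efficacy Analysis): "The model will include fixed, categorical effects for treatment, site, visit, and treatment-by-visit interaction". The synopsis then applies the same MMRM to the key secondary endpoints.

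Protocol 8.1.3.1: "The model will include fixed, categorical effects for treatment, country, visit, and treatment-by-visit interaction". The two sentences differ only in that factor.

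SAP 9.2: "The model will include the fixed effects of treatment, country and visit, with baseline score as a covariate". It goes on to include baseline-by-visit but does not list treatment-by-visit.

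Protocol 8.3: "Subject randomization will be stratified by country".

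Country is also the factor in the ANCOVA of Protocol 8.1.3.2, in the ANCOVA and the CGI-C/PGIC ANOVA of SAP 9.3, and in the subgroup model of SAP 9.6. Site as a model factor appears only in the synopsis. SAP section 12 states that the analysis is unchanged from Protocol Amendment 4 and does not mention the difference.

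On scale, the synopsis says: "This study will be conducted at approximately 40 – 50 sites in approximately 10 countries worldwide". Protocol 8.3 says: "Approximately 88 subjects will be enrolled into the study and randomized in a 1:1 ratio to either optimized medical treatment or LCIG".

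**The concern.** Both primary endpoints and the key secondaries rest on this model, and current protocol text gives it in two forms. The choice of factor matters here because sites are so small: 88/50 = 1.8 to 88/40 = 2.2 subjects per site. In a single-visit analysis with fixed site effects, a site with one subject, or with subjects from one arm only, adds nothing to the treatment contrast. Randomization is not stratified by site, so nothing prevents one-arm sites. A country factor has about 10 levels, matches the stratification and costs almost nothing.

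**Working it through.** **1. The plan's own figure.** Inputs from Protocol 8.2 and SAP 4.3:
- NMSS improvement 24.8 v 8.2 (difference 16.6), SD 24.
- PDSS-2 improvement 13.1 v 4.3 (difference 8.8), SD 12.2.
- Correlation between endpoints 0.5; two-sided Hochberg at 0.05; success on at least one endpoint.

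Simulation with two-sample t tests and no site or country term gives 90.6% for 37 per group. It also gives 90.6% for 44 per group with change set to zero for a random 10%. The plan states 90% for both, so its figures reproduce.

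**2. Information lost to site effects, closed form.** With fixed site effects and one visit, the information on treatment is proportional to the sum over sites of n1·n0/n. Under simple 1:1 allocation the expected value for a site of size n is (n − 1)/4. Summed over S sites this is (N − S)/4, against about N/4 unadjusted. The share kept is therefore (N − S)/N.
- N = 88: 48/88 = 55%, 43/88 = 49%, 38/88 = 43% for 40, 45 and 50 sites.
- N = 80: 40/80 = 50%, 35/80 = 44%, 30/80 = 38%.

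N = 80 is roughly the evaluable number after the plan's 10% allowance (44 × 0.9 = 39.6 per group).

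**3. The same with country-stratified randomization.** Assumptions not in the documents: blocks of 4 within 10 countries, and every site enrolling. The analysis is of a single visit without baseline adjustment. Information is relative to the country model; power is for at least one primary endpoint.

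| N | Sites | Information kept | Loss | Power, site model |
|---|---|---|---|---|
| 88 | 40 | 0.616 | 38% | 0.77 |
| 88 | 45 | 0.554 | 45% | 0.74 |
| 88 | 50 | 0.487 | 51% | 0.66 |
| 80 | 40 | 0.569 | 43% | 0.71 |
| 80 | 45 | 0.500 | 50% | 0.62 |
| 80 | 50 | 0.426 | 57% | 0.57 |

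A second simulation gave site-model powers within about 0.02 of these. Spreading subjects unevenly over the same number of enrolling sites barely changes the loss (58% at worst). The range is therefore roughly 40 to 58%. The country model keeps about 98 to 100% of the unadjusted information, with power 0.92 to 0.95.

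**4. Sensitivity of the site-model result.**
- *Baseline adjustment.* Both stated models adjust for baseline. With equal SDs σ and baseline–follow-up correlation ρ, the variance of change is 2σ²(1 − ρ), and after adjustment it is σ²(1 − ρ²). At ρ = 0.5 these are σ² and 0.75σ², a 25% cut. The plan gives 0.5 for PDSS-2 only; using it for NMSS is an assumption. Site-model power becomes about 0.69 to 0.88.
- *Sites that enrol nobody.* With an uneven (Dirichlet) spread, about 27 to 32 of the 40 to 50 sites enrol. The share of unadjusted information kept runs from 0.756 (N = 88, 40 planned sites) to 0.679 (N = 80, 50 planned sites), a loss of about 25 to 32%. Power is about 0.79 to 0.88. With baseline adjustment as well, power at N = 80 is 0.89 to 0.92.
- *Three visits.* In the MMRM, one-arm sites still inform between-visit contrasts. With within-subject correlation 0.3 to 0.9, covariance taken as known and all sites enrolling, the share kept is 46 to 69% (N = 88) or 40 to 65% (N = 80). Power is 0.64 to 0.83 or 0.53 to 0.76.
- *Real between-site variance.* At intraclass correlation 0.1 to 0.2, N = 88 and 45 sites, site-model power is 0.78 to 0.82.

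**The case against.** The strongest reply is that nobody would run the site model. The detailed section, the SAP's primary, ANCOVA, ANOVA and subgroup models, and the stratification all say country. SAP 4.4 treats database lock as still to come, so the country model is specified in advance. This stands, and it sets the severity.

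It also disposes of three stronger readings that a reader might infer:

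- *The primary model is left open until the data are seen.* The documents do not support this. One word in the synopsis stands against every detailed statement of the analysis.
- *The 90% power claim is contradicted.* The sample-size text names no site or country term, its figures reproduce, and the country model meets 90%. The shortfall belongs only to the model that the body and SAP do not use.
- *Site adjustment would cost half the information, without qualification.* That holds only if nearly all 40 to 50 sites enrol, and the documents give only an approximate planned number.

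What the reply does not remove is that the synopsis is current protocol text and disagrees with the body. The SAP's statement of no change from Amendment 4 is true of section 8.1.3.1 but not of the synopsis.

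**Conclusion.** The inconsistency is certain, and the documents show which side is wrong: site in the synopsis should be country. If the synopsis model were run with all 40 to 50 sites enrolling, it would lose roughly 40 to 58% of the treatment information. Power would be about 0.57 to 0.77 over N = 80 to 88 (single visit, no baseline adjustment), or about 0.69 to 0.88 with a 25% cut in residual variance. With uneven enrolment and many empty sites the loss is about 25 to 32% and power about 0.79 to 0.88; only with baseline adjustment added does it come near 90%. All of these rest on assumed site enrolment and block size. The country model keeps about 99% of the information and meets the stated power.

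This is a minor correction to make before database lock. It does not put the planned analysis in doubt.

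Changing that word alone will not align the documents, because two other differences remain:
- SAP 9.2 omits the treatment-by-visit interaction that both protocol versions include, although it too makes Week 26 the primary contrast and calls tests at other visits secondary.
- CGI-C, a key secondary, is analysed by MMRM in the synopsis and Protocol 8.1.3.2 but by ANOVA in SAP 9.3. Protocol Table 3 and SAP Table 1 give it a single post-baseline assessment, at Week 26 or early discontinuation.

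**What to change.** 1. In the protocol synopsis, Primary Efficacy Analysis, replace site with country, so that the primary and key secondary models agree with section 8.1.3.1 and the stratification.
2. In SAP section 12, record that the synopsis named site and that country is the specified factor.
3. In SAP 9.2, list the treatment-by-visit interaction.
4. State one model for CGI-C in both documents. With one assessment per subject there are no repeated measures to model, so the SAP's ANOVA fits the schedule and the protocol text is the simpler one to change.

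The cost is a few words at the next amendment and SAP revision, before database lock. No new data are needed and the sample size does not change. Programs already written to SAP 9.2 need only a check that treatment-by-visit is in the model.

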1.3 List of Abbreviations and Definition of Terms

Abbreviations

AE	adverse event
AESI	adverse event of special interest
β-HCG	beta-human chorionic gonadotropin
BUN	blood urea nitrogen
CFR	Code of Federal Regulations
CGI-C	Clinical Global Impression – Change
CHMP	Committee for Medicinal Products for Human Use
CMQ	Company MedDRA Query
CNE or DSS	Clinical Nurse Educator – Duodopa Study Specialist
COMT	Catechol O methyltransferase
CR	controlled release
CS	Clinically Significant
C-SSRS	Columbia-Suicide Severity Rating Scale
CTCAE	Common Terminology Criteria for Adverse Events
DBP	diastolic blood pressure
DBS	Deep Brain Stimulation
DDI	DOPA decarboxylase inhibitor
DO	Doctor of Osteopath
DSM	Diagnostic and Statistical Manual of Mental Disorders
DSS	Duodopa Study Specialist
EC	Ethics Committee
ECG	Electrocardiogram
eCRF	electronic case report form
EQ VAS	EuroQol Visual Analogue Scale
FDA	Food and Drug Administration
GCP	Good Clinical Practice
GDS-15	Geriatric Depression Scale
GDSM	Global Drug Supply Management
GI	gastro-intestinal
GMP	Good Manufacturing Practice
HLGT	high level group term

HLT	high level term
HRQoL	health related quality of life
IB	Investigator's Brochure
ICH	International Conference on Harmonization of Technical Requirements for Registration of Pharmaceuticals for Human Use
IEC	Independent Ethics Committee
IND	Investigational New Drug Application
IV	Intravenous
IR	Immediate Release
IRB	Institutional Review Board
IRT	Interactive Response Technology
LAR	Legally acceptable representative
LCIG	levodopa-carbidopa intestinal gel
LC-CR	Levodopa/Carbidopa-Continuous Release
LC-IR	Levodopa/Carbidopa-Immediate Release
LLT	lowest level term
MAO-A	monoamine oxidase A
MAO-B	monoamine oxidase B
MAO Inhibitors	monamine oxidase inhibitors
Max	Maximum
MD	Doctor of Medicine
MedDRA	Medical Dictionary for Regulatory Activities
MIDI	Minnesota Impulsive Disorders Interview
Min	Minimum
MMA	methylmalonic acid
MMSE	Mini-Mental State Examination
MMRM	Mixed-effect Repeated-Measures Model
MoCA	Montreal Cognitive Assessment
NCS	Not Clinically Significant
NDC	National Drug Code
N-J	Nasojejunal
NMS	Non-motor symptoms
NMSS	Non-Motor Symptom Scale
NP	Nurse Practitioner
NONMEM [®]	nonlinear mixed effects modeling

3-OMD	3-O-methyldopa
OMT	Optimized Medical Therapy
PA	Physician Assistant
PAS	Parkinson Anxiety Scale
PC	Product Complaints
PCS	Potentially Clinically Significant
PD	Parkinson's disease
PDQ-8	Parkinson's Disease Questionnaire-8
PDQ-39	Parkinson's Disease Questionnaire-39
PDSS-2	Parkinson's Disease Sleep Scale
PEG	percutaneous endoscopic gastrostomy
PEG-J	percutaneous endoscopic gastrostomy – with jejunal extension
PGIC	Patient Global Impression of Change
PhD	Doctor of Philosophy
PK	Pharmacokinetic
PLMS	periodic limb movements of sleep
PT	preferred term
QoL	Quality of Life
RBD	behavioral sleep disorder
REM	rapid eye movement
RLS	restless leg syndrome
RSI	Reference Standard Information
SAP	Statistical Analysis Plan
SAQ	Sleep Attacks Questionnaire
SBP	systolic blood pressure
SD	standard deviation
SGOT/AST	aspartate aminotransferase
SGPT/ALT	alanine aminotransferase
SmPC	Summary of Product Characteristics
SMQ	Standard MedDRA Query
SOC	system organ class
SOP	standard operating procedure
TA MD	Therapeutic Area Medical Director
UKPDS	United Kingdom Parkinson's Disease Society

UPDRS	Unified Parkinson's Disease Rating Scale
WHO	World Health Organization
WOCBP	Women of Child Bearing Potential

Definition of Terms

Dose Titration Diary	A paper record used to document the date, time and dose changes during subject titration.
Duodopa Study Specialist	An external nurse specialist who may be provided by the Sponsor to assist the Investigator with initiation and titration of LCIG.
LCIG Cassette Use Form	A paper record used to document dates of individual LCIG cassette use.
LCIG Optimization	Following the introduction of LCIG, maximizing the functional "On" time and minimizing the number of "Off" (bradykinesia) episodes during the day and the total time the subject is "Off;" in addition, minimizing the "On" time with troublesome dyskinesia.
LCIG Prescription Record	A paper record of the LCIG pump settings for a subject's morning dose, flow rate and extra doses that is recorded at every visit by the site.
Optimized Treatment	The maximum therapeutic effect obtained with pharmacological antiparkinsonian therapies when no further improvement is expected regardless of any additional manipulations of levodopa and/or other antiparkinsonian medication.
PRN	Per Diem or As Needed.
Subject Dosing Worksheet	A paper record used to document the date, time and dose of LCIG and levodopa-carbidopa tablets used by the subject during the initial titration period.
